7.1.2 Treatment Period

The treatment period begins with the completion of all Baseline evaluations and the initiation of trial drug treatment on Study Day 1 and continues through to the completion of the treatment period at the end of Month 24 Visit.

7.1.3 Baseline Visit (Study Day 1) (+7 days)

Once a subject has met the eligibility criteria and is ready to begin treatment, he/she will be administered the IMP. Baseline is defined as the day on which the first dose of IMP is administered (Day 1 of treatment).

The following procedures will be performed at Baseline:

- Review of inclusion/exclusion criteria
- Review of subject diary
- Physical examination* including vital signs (including blood pressure, heart rate, temperature)
- MRI assessment** (see Section 7.3.1)
- Neurological examination including SDMT, EDSS/KFS, 9HPT and T25FW***
- Number of relapses within the last 12 months (see Section 7.3.3)

CCI

- Urine pregnancy test (for female subjects of child-bearing potential only)
- Administration of trial medication
- Assessment of AEs, concomitant medications and concomitant procedures
- Weight measurement and assignment of IMP via IRT

*** In this protocol, symptoms and signs of relapse or worsening of MS since the previous visit will usually be captured in the context of the efficacy assessment, and recorded on the relapse**

module of the eCRF. Therefore, symptoms, relapses or worsening of MS will not be considered as AEs nor captured on the AE module of the eCRF unless considered possibly or probably related to the IMP (i.e., worsening is not consistent with the anticipated natural progression of the disease)

**** There will be a gap of atleast 4 weeks between a MRI at screening and Baseline. MRI scans will be assessed for efficacy and safety purposes.**

*****If the neurological examination at the Screening visit is conducted within 10 days of Study Day 1, and the subject reports no change in status, no neurological examination needs to be repeated on Baseline (Study Day 1).**

If the lymphocyte count at screening is done before 4 weeks from Baseline, it should be repeated within 4 weeks of Baseline

Each subject will be given a diary form to record the dose, date and time of each administration of IMP, AEs, concomitant medications and procedures (see [Appendix 10: Example of Subject Diary](#)). The subject diary entries must be reviewed by the trial coordinator(s)/nurse(s) with the subject to clarify any discrepancies and ensure proper completion. This review must be completed at each visit and the review recorded in the subject's clinic visit notes. The appointed designee will enter in the eCRF what each subject records on his/her subject form and any information that is obtained after subsequent questioning of the subjects.

Since accurate drug dosing is based on weight, prior to dispensing the treatment medication at Day 1 for treatment course Year 1 and Year 2, the subject's weight should be accurately assessed.

Once all procedures and assessments for this visit are completed, an appointment for the next visit will be made and the subject will be discharged.

7.1.4 Month 1 Visit (± 7 days)

The following procedures and assessments will be performed at the Month 1 visit:

- Review of subject diary
- Weight measurement and assignment of IMP via IRT
- MRI assessment (see Section 7.3.1)
- Administration of trial medication
- Assessment of AEs, concomitant medications and concomitant procedures

Once all procedures and assessments for this visit are completed, an appointment for the next visit will be made and the subject will be discharged.

7.1.5 Month 2 Visit (± 7 days)

The following procedures and assessments will be performed at the Month 2 visit:

- Review of subject diary
- MRI assessment (see Section 7.3.1)
- Assessment of AEs, concomitant medications and concomitant procedures
- Blood samples for safety analysis at local laboratory*

*Lymphocyte count will be checked locally after 2 months of starting treatment. If the lymphocyte count is below 500 cells/mm³, it should be actively monitored until values increase again.

Once all procedures and assessments for this visit are completed, an appointment for the next visit will be made and the subject will be discharged.

7.1.6 Month 3 Visit (±7 days)

The following procedures and assessments will be performed at the Month 3 visit:

- Review of subject diary
- MRI assessment (see Section 7.3.1)

CCI

- Assessment of AEs, concomitant medications and concomitant procedures

Once all procedures and assessments for this visit are completed, an appointment for the next visit will be made and the subject will be discharged.

7.1.7 Month 6 Visit (±7 days)

The following procedures and assessments will be performed at the Month 6 visit:

- Review of subject diary
- Physical examination including vital signs (including blood pressure, heart rate, temperature)
- MRI assessment (see Section 7.3.1)
- Blood samples for safety analysis at local laboratory *
- Neurological examination including SDMT, EDSS/KFS, 9HPT and T25FW

CCI

- Assessment of AEs, concomitant medications and concomitant procedures

*Lymphocyte count will be checked locally after 6 months of starting treatment. If the lymphocyte count is below 500 cells/mm³, it should be actively monitored until values increase again. Once all procedures and assessments for this visit are completed, an appointment for the next visit will be made and the subject will be discharged.

7.1.8 Month 12 Visit (± 7 days)

The following procedures and assessments will be performed at the Month 12 visit:

- Review of subject diary
- Physical examination including vital signs (including blood pressure, heart rate, temperature)
- Serology (HIV, Hepatitis C and B) and TB test
- MRI assessment (see Section 7.3.1)
- Neurological examination including SDMT, EDSS/KFS, 9HPT and T25FW
- Number of relapses (see Section 7.3.3)
- Blood samples for safety analysis at local laboratory (Section 7.4.3)*

CCI

- Urine pregnancy test (for female subjects of child-bearing potential only)
- Administration of trial medication and provision of trial medication intake for Month 13
- Weight measurement and assignment of IMP via IRT
- Assessment of AEs, concomitant medications and concomitant procedures

*Lymphocyte count should be at least 800 cells/mm³ before initiating cladribine in Year 2. If necessary, the treatment course in Year 2 can be delayed for up to 6 months to allow for recovery of lymphocytes. If this recovery takes more than 6 months, the subject should not receive cladribine anymore.

Once all procedures and assessments for this visit are completed, an appointment for the next visit will be made and the subject will be discharged.

7.1.9 Month 14 Visit (± 7 days)

- Review of subject diary
- Blood samples for safety analysis at local laboratory*
- Assessment of AEs, SAE's concomitant medications and concomitant procedures

*Lymphocyte count will be checked locally after 2 months of starting treatment. If the lymphocyte count is below 500 cells/mm³, it should be actively monitored until values increase again.

7.1.10 Month 15 Visit (± 7 days)

The following procedures and assessments will be performed at the Month 15 visit:

- Review of subject diary

- MRI assessment (see Section 7.3.1)

CCI

- Assessment of AEs, concomitant medications and concomitant procedures

Once all procedures and assessments for this visit are completed, an appointment for the next visit will be made and the subject will be discharged.

7.1.11 Month 18 Visit (± 7 days)

The following procedures and assessments will be performed at the Month 18 visit:

- Review of subject diary
- Physical examination including vital signs (including blood pressure, heart rate, temperature)
- MRI assessment (see Section 7.3.1)
- Neurological examination including SDMT, EDSS/KFS, 9HPT and T25FW

CCI

- Blood samples for safety analysis at local laboratory*
- Assessment of AEs, concomitant medications and concomitant procedures

*Lymphocyte count will be checked locally after 6 months of starting treatment. If the lymphocyte count is below 500 cells/mm³, it should be actively monitored until values increase again. Once all procedures and assessments for this visit are completed, an appointment for the next visit will be made and the subject will be discharged.

7.1.12 Final Visit / Early Termination (Month 24 Visit [± 7 days])

To complete the trial, the subject should return for a final evaluation at the end of Month 24. In the event of early discontinuation from the trial, the subject should return for the Month 24 procedures outlined below. The reason for early discontinuation should be accurately assessed and entered into the eCRF.

The following procedures and assessments will be performed at the end of Month 24 visit:

- Review of subject diary
- Physical examination including vital signs (including blood pressure, heart rate, temperature)
- MRI assessment (see Section 7.3.1)
- Neurological examination including SDMT, EDSS/KFS, 9HPT and T25FW.
- Number of relapses (see Section 7.3.3)

- Blood samples for safety analysis (only lymphocyte count) at local laboratory (see Section 7.4.3)

CCI

- Assessment of AEs, concomitant medications and concomitant procedures

7.1.13 Unscheduled Visits

A subject may return for an unscheduled visit at the discretion of the Investigator to undergo additional safety evaluations (i.e., laboratory retesting, AE assessments), or for additional neurological evaluations following a relapse (see Section 7.3.3). The data from unscheduled visits will be collected in the eCRF.

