7.3.3 Relapse Evaluation

Relapse evaluation will be completed at Baseline, end of Month 12 and 24 or following early termination and whenever necessary.

Note that this section defines relapse as a variable to be measured during the course of the trial.

All the following criteria are to be met for establishing an MS clinical relapse:

1. Neurological abnormality, either newly appearing or re-appearing, with abnormality specified by both
 - a. Neurological abnormality separated by at least 30 days from onset of a preceding clinical event,
 - and*
 - b. Neurological abnormality lasting for at least 24 hours
2. b) Absence of fever or known infection (fever with temperature (axillary, orally or intrauricular) > 37.5°C / 99.5 °F)

3. Objective neurological impairment, correlating with the subject's reported symptoms, defined as either
 - a. Increase in at least one of the functional system (FS) scores of the EDSS
 - or
 - b. Increase of the total EDSS score

The occurrence of paraesthesia, fatigue, mental symptoms, and/or vegetative symptoms without any additional symptom will not be classified as an MS clinical relapse.

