7.3.3.1 Procedure for Relapse Evaluation

The subject will be instructed to contact immediately the treating physician if he/she develops new or re-occurring or worsening neurological (including visual) symptoms. At each scheduled visit, the subject will be asked whether any such symptoms have occurred.

Upon reporting symptoms indicative of a relapse, the investigator will assess whether the symptoms occur in the presence of fever or infection (in case of an unscheduled phone-contact, the treating physician may simply ask the subject). If fever or infection is excluded, the Investigator must arrange for a neurological examination as soon as possible, at the latest within 7 days following the reporting of the event. If fever or infection cannot be excluded, the neurological examination by the Investigator will have to be postponed until the fever or the infection have ceased (provided, that the symptoms indicative of a relapse are still present).

Based on the respective EDSS/KFS scores, in conjunction with the results from previous examinations, the Investigator will assess whether the EDSS criterion for a relapse during the course of the trial is fulfilled.

Note: Since relapses may impact on the results of MRI scans, the occurrence of a relapse may cause the postponement of MRI scans (Section 7.3.1).

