- 1 year = 365.25 days.

Time window

- Day 1 is the day of start of study medication, the day before is Day - 1 (no Day 0 is defined),
- Study day / Treatment day is defined relative to Day 1.

The Visit schedule is defined as follows:

- 1 month = 30 days,
- 1 year = 360 days,

relative to the start date of the Baseline Visit for Treatment Course 1 and relative to the start date of the Month 12b Visit as defined in the eCRF (see also Section 15.3) for Treatment Course 2.

In each analysis, should assessments be delayed, subjects' assessment data will be treated as though it occurred at the time point specified (i.e., out of Visit windows will be not excluded or adjusted for any analyses) and inferences will be conducted accordingly. Thus, further time windows will not be specified.

All observations from unscheduled Visits will be included only in the analyses of Visit independent summaries (e.g. counts of events, progressions or worst value during Treatment Period) unless for the unscheduled Visits prior to start of study medication and the last assessment available. In case of unscheduled Visits prior to start of study medication, these will be considered to define Baseline. In the last missing case the ET Visit will be imputed by the unscheduled Visit.

The assessments of the ET Visit will be mapped to the nearest planned post-Baseline Visit with a missing assessment before or after the ET Visit of the individual assessment for all statistical analyses and descriptive summaries. As not all assessments of the ET are performed at each Visit, the different assessments of the ET can be assigned to different Visits. If the duration (in days) between the ET Visits and two missing planned Visits are equal, then the assessment will be assigned to the later Visit.

Handling of missing data

Unless otherwise specified in respective sections, missing data will not be replaced.

The handling of missing covariate and stratification factor information is described below.

The handling of missing DMD end date is described in Section 12.

Incomplete or missing onset dates of relapses from "MS Relapse Report" will be imputed as follows:

- In cases where the onset date is partially missing but the onset month and year, or the onset year are equal to the start of study medication or the date is missing then the onset date will be replaced by the start date of study medication.

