The increase will be defined as sustained when it occurs on two post-Baseline Visits, which are at least 166 days (6 months × 30 - 14 days Visit Window) apart and no observations at any other Visit (including unscheduled Visits) in between are less than the defined increase.

The occurrence of a 6MCDP is defined as:

- Yes: sustained increase in EDSS score that started during the Treatment Period,
- No: at least 2 post-Baseline EDSS assessments that are 166 (or more) days apart are available and no sustained EDSS progression that started during the Treatment Period,
- Unknown: Otherwise.

Start date of the 6MCDP is the start date of the first sustained increase in EDSS.

MRI activity:

- Yes: At least one T1 Gd+ at any scan assigned to Month 6, Month 12, Month 18, Month 24 Visit, or at least one active T2 during any of the following Periods: Baseline to Month 6, Month 6 - Month 12, Month 12 - Month 18, Month 18 – Month 24 Visits.
- No: T1 Gd+ = 0 at all scans assigned to Month 6, Month 12, Month 18, Month 24 Visit that have a value and at least one T1 Gd+ value from Month 18 or Month 24 Visit available, and all active T2 = 0 during any of the following Periods: Baseline - Month 6, Month 6 - Month 12, Month 12 - Month 18, Month 18 - Month 24 Visits that have a value and at least one active T2 value from periods Month 12 - Month 18 or Month 18 - Month 24 Visits available.
- Unknown: Otherwise.

CCI [REDACTED]

[REDACTED]

[REDACTED]

[REDACTED]

CCI [REDACTED]

CCI [REDACTED]

Brain Atrophy

- Yes: Annualized percentage brain volume change during the Treatment Period < -0.4% (see Section 14.3.11),
- No: Annualized percentage brain volume change during the Treatment Period ≥ -0.4%,
- Unknown: Otherwise.

Analysis of NEDA

NEDA and its components will be analyzed with a logistic regression with adjusting factors age (in years) and EDSS at Baseline (≤3, >3).

Analysis (Analysis Set)	Derivation	Statistical Analysis Methods	Missing data handling
Tertiary endpoint: NEDA at 24 months			
Tertiary (FAS)	NEDA-3 during Treatment Period	Logistic regression: Adjusting factors: 
 • Age (in years), • EDSS at Baseline (≤3, >3). Estimated probability and corresponding Standard Errors (SE) will be presented including 2-sided p-values and 95% CIs.	Unknown status: Subjects with an unknown status will be excluded from the logistic regression. Missing covariate or stratification information will be imputed as specified in Section 9.

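### An EDSS score taken during a relapse may confirm 6-month disability progression (6MCDP), so two transient relapses about six months apart can be coded as sustained

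*Protocol*

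**What the plan says.** Under Protocol 7.3.3 a relapse needs objective impairment, either "Increase in at least one of the functional system (FS) scores of the EDSS" or "Increase of the total EDSS score". When one is suspected and fever or infection is excluded, Protocol 7.3.3.1 says "the Investigator must arrange for a neurological examination as soon as possible, at the latest within 7 days following the reporting of the event". Protocol 7.1.13 provides for unscheduled visits "or for additional neurological evaluations following a relapse (see Section 7.3.3). The data from unscheduled visits will be collected in the eCRF". Relapse-time EDSS scores will therefore be in the database.

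The rules that decide how they are used are in the SAP:

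- Section 9 (Time window): "All observations from unscheduled Visits will be included only in the analyses of Visit independent summaries (e.g. counts of events, progressions or worst value" over the treatment period.
- Section 14.3.12 (6MCDP): "The increase will be defined as sustained when it occurs on two post-Baseline Visits, which are at least 166 days".
- The same sentence adds a safeguard: "no observations at any other Visit (including unscheduled Visits) in between are less than the defined increase".

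The required rise is 1.5 points from a Baseline EDSS of 0, 1.0 point from 0.5–4.5, and 0.5 point from 5 or more. Neither the SAP nor the protocol's own definition of confirmed progression (7.3.2.2) says whether a relapse-time score may confirm. SAP 14.3.12 analyses 6MCDP both as a NEDA-3 component and on its own, by logistic regression in the FAS.

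**The concern.** Confirmation over six months is meant to separate lasting disability from the rise and recovery of a relapse. If the second score may itself come from a relapse, two separate and fully recovered events can meet the rule. The stand-alone 6MCDP result would then overstate progression and partly repeat the relapse endpoint, in a population selected for high relapse activity.

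There is a further route. SAP Section 9 maps Early Termination assessments to the nearest planned visit with a missing assessment, and lets an unscheduled visit stand in for a missing Early Termination visit. A subject who starts another DMD after a relapse leaves the trial after that visit (Protocol 5.5.1 and 6.5.1.4). A score taken close to a relapse can thus appear in the data as a scheduled one.

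**Working it through.** **1. The plan's own figure.** 6 × 30 − 14 = 166 days, as in SAP 14.3.12. Scheduled EDSS visits at Months 6, 12, 18 and 24, each ±7 days, are 180 ± 14 = 166 to 194 days apart.

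**2. The rule applied literally** (raised = at or above the threshold):

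| Scores by study day | Test | Coded |
|---|---|---|
| 345 raised (relapse), 360 raised (Month 12), recovery, 515 raised (second relapse), 540 normal (Month 18) | 515 − 345 = 170 ≥ 166; only score between is raised | Sustained |
| 180 normal, 185 raised, 355 raised, 360 normal | 355 − 185 = 170 ≥ 166; no score between | Sustained |
| 270 raised, 360 normal, 450 raised | 450 − 270 = 180, but a lower score lies between | Not sustained |
| 270 raised, Month 12 missed, 450 raised | 180; no score between | Sustained |
| 185 raised, 240 normal (recovery examination), 355 raised | 170, but a lower score lies between | Not sustained |

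The error is real but needs particular timing: both relapses near the ends of one inter-visit interval, a scheduled visit that falls while EDSS is still raised, or a missed visit. A delayed Course 2 also helps it, because Year 2 visits run from Month 12b and the Month 12 to Month 18 gap widens.

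**3. Which visits drive it.** Simulated subjects each had two reversible, threshold-meeting relapses 180 days apart. Assumptions: uniform onset, relapse examination 1–7 days after onset, no missed visits, no recovery visits. Share falsely coded as 6MCDP, by duration of the rise:

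| Rule | 14 days | 30 days | 60 days | 90 days |
|---|---|---|---|---|
| SAP as written | 6% | 15% | 32% | 49% |
| Confirming visit must be scheduled | 5% | 14% | 31% | 48% |
| Scheduled visits only, both ends | 3% | 12% | 29% | 47% |

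At a 180-day gap, excluding unscheduled visits altogether removes about 2–3 percentage points; at 166 days it removes about 10–11. For a 30-day rise, the rate under the SAP rule by gap is 7% (150 days), 19% (166), 15% (180), 7% (194), 1% (210) and 0% (240). A recovery visit 45 days after onset brings it to 0% at 166, 180 and 194 days. These percentages are conditional on having two such relapses and are not trial-level rates.

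**4. Trial-level size.** Assumptions, none from the documents: Poisson relapses over 720 days, 60% of them raising EDSS past the threshold, gamma-distributed reversible rises, relapse examination 0–7 days after onset, and no true progression. False 6MCDP over 24 months:

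| Relapses per year | Mean rise | SAP rule | Relapse-free confirming score |
|---|---|---|---|
| 0.4 | 45 days | 0.44% | 0.16% |
| 1.0 | 45 days | 2.46% | 0.79% |
| 0.4 | 90 days | 2.29% | 1.78% |
| 1.0 | 90 days | 8.95% | 5.88% |

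Of 265 planned subjects, the 45-day rows give 265 × 0.0044 = 1.2 falling to 265 × 0.0016 = 0.4, and 265 × 0.0246 = 6.5 falling to 265 × 0.0079 = 2.1. With a recovery examination after each relapse, the SAP-rule figures in those rows drop to 0.16% and 1.03%. Also requiring the confirming visit to be scheduled gave the same rates as the relapse-free condition alone.

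**The case against.** The strongest reply is that the SAP already protects against this. Any lower score in between, unscheduled visits included, breaks confirmation, and Protocol 7.1.13 itself provides for examinations after a relapse. That stands: it blocks many relapse pairs, and unscheduled recovery visits reduce the error. It does not block pairs with no lower score between them.

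The 90-day rows should also not be read as the size of this mechanism. In them, 1.68 of the 2.29 points and 5.66 of the 8.95 points involve a single rise lasting at least 159 days (166 − 7). A rise of nearly six months from one event is broadly what a 6-month rule is meant to count. That stands too, so only the 45-day rows are used for size.

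A reader might infer that unscheduled visits are the cause. Protocol 7.1.13 only collects the data, and step 3 shows that scheduled visits falling within a relapse produce most of the effect at a 180-day gap. The gap in the plan is the lack of any relapse condition on the confirming score.

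A reader might also infer that confirmed T25FW and 9HPT progression are inflated, since SAP 14.3.13 uses the same two-visit wording. The documents do not require either test at a relapse visit, the relapse assessment rests on EDSS/KFS, and no effect on them has been shown.

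Finally, 6MCDP is tertiary and exploratory in a single-arm trial, and the bias is unfavourable to the product. That limits the importance but does not make the coding right.

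**Conclusion.** The point holds as a small defect in one derivation rule. A relapse-time EDSS score may confirm 6MCDP, and transient relapses about 166–194 days apart can be coded as sustained when no lower score intervenes. With 45-day reversible relapses the false rate is about 0.4–0.5% at 0.4 relapses per year and about 2.5% at 1.0, and lower with recovery examinations. Relapse rate, duration and the share of relapses passing the threshold are all assumed.

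It would be tempting to conclude that NEDA is distorted. It largely is not: a qualifying relapse already makes NEDA-3 'No', and NEDA-4 and NEPAD build on NEDA-3. They could change through this route only if the relapses were not classed as qualifying. The effect falls on the stand-alone 6MCDP analysis.

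**What to change.** Add to SAP 14.3.12: *The confirming EDSS assessment (scheduled, unscheduled, or mapped/imputed Early Termination) must not fall within 30 days after the onset of a relapse; scores obtained within that window may start, but not confirm, a sustained increase.* Report the current rule as a sensitivity analysis.

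The 30 days are an analysis convention borrowed from the separation of clinical events in Protocol 7.3.3; they are not a recovery time. Rises that outlast the window can still confirm, which is why a residual rate remains in step 4. The condition may be applied to T25FW and 9HPT for consistency.

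The cost is one sentence and a small programming change using relapse onset dates already collected. A few late worsenings, such as at a Month 24 visit soon after a relapse, will stay unconfirmed; the sensitivity analysis shows how many.
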